#### **8.1.4.1.3 Other Efficacy Variables**

Additional efficacy variables are listed in Section [5.3.3.1.3](#) and will be summarized for all visits. For binary endpoints, frequencies and percentages will be reported for each treatment group. For continuous endpoints, the change from baseline mean, standard deviation, median, and range will be reported for each treatment group.

---

#### **8.1.4.1.4 Multiplicity Control for the Primary and Ranked Key Secondary Endpoints**

In order to preserve Type I error, a step-down approach will be used to test the primary and ranked key secondary endpoints where statistical significance can be claimed for a lower ranked endpoint only if the previous endpoints in the sequence meet the requirements of significance.

#### **8.1.4.1.5 Imputation Methods**

The following methods will be used for missing data imputation:

**Observed Cases (OC):** The OC analysis will not impute values for missing evaluations, and thus a subject who does not have an evaluation on a scheduled visit will be excluded from the OC analysis for that visit.

**Multiple Imputation (MI):** The MI analysis imputes missing data multiple times under appropriate random variation and thus generates multiple imputed "pseudo-complete" datasets. Results will be aggregated across the multiple imputed datasets, overcoming drawbacks of the single imputation methods.

**Non-Responder Imputation (NRI):** NRI applies to binary endpoints only. In NRI analysis, subjects who prematurely discontinue study drug will be considered non responders after discontinuation.

The NRI approach will serve as the primary analysis approach for key binary endpoints. The MI approach will serve as the primary analysis approach for key continuous endpoints. Sensitivity analyses based on OC will also be conducted for key endpoints.

#### **8.1.4.2 Long-Term Efficacy Analysis for Period 1 and Period 2 Combined**

The efficacy endpoints of long-term efficacy analysis are listed in Section 5.3.3.2 and will be summarized for all visits.

Long-term efficacy by time point will be summarized using descriptive statistics. For binary endpoints, frequencies and percentages will be summarized. For continuous endpoints, the mean and standard deviation will be reported.

### **8.1.5 Safety Analyses**

#### **8.1.5.1 General Considerations**

Safety analyses will be carried out using the Safety Analysis Set. Analyses will be conducted for Period 1 alone, as well as for Period 1 and Period 2 combined.

Safety analyses are based on treatments actually received. Safety will be assessed by AEs, physical examination, laboratory assessments, ECG, and vital signs. Frequency tables and lists of subjects with treatment-emergent AEs by preferred term as in the Medical Dictionary for Regulatory Activities (MedDRA) dictionary, by system organ class, by severity, and by relationship to the study drug as assessed by the Investigator will be provided. The changes from baseline in vital signs, physical examination results, and clinical laboratory values will be analyzed. Shift of laboratory values from baseline to defined time points will be tabulated.

Missing safety data will not be imputed.

#### **8.1.5.2 Analysis of Adverse Events**

Unless otherwise specified, the following conventions apply for both the Period 1 safety analysis and the combined safety analysis of Period 1 and Period 2.

##### **8.1.5.2.1 Treatment-Emergent Adverse Events (TEAE)**

AEs will be coded using MedDRA. A TEAE is defined as AE that began or worsened in severity after initiation of study drug.

AEs starting more than 30 days following the last dose of study drug will not be included in summaries of TEAEs. For subjects who continued into Period 2, AEs that are reported in Period 2 will be captured in the combined safety analysis of Period 1 and Period 2.

As a general safety summary, the number and percentage of subjects experiencing TEAEs will be summarized for each treatment group for the following AE categories:

- All AEs;
- All severe AEs;
- All reasonably possibly related AEs;
- All SAEs;
- Frequent AEs (reported in 2% of subjects or more in any treatment group);
- Frequent reasonably possibly related AEs (reported in 2% of subjects or more in any treatment group);
- Discontinuations due to AEs;
- Death.

Additional AEs may be considered for tabulation/summary based on recommendations from Clinical and Safety as deemed appropriate.

TEAEs will be summarized and presented by system organ classes (SOCs) and preferred terms (PTs) using MedDRA. The SOCs will be presented in alphabetical order, and the PTs will be presented in alphabetical order within each SOC.

TEAE will also be summarized by maximum severity and by maximum relationship.

The AEs of special interest (including but not limited to serious infection, opportunistic infection, herpes zoster, TB, gastrointestinal perforations, malignancies, adjudicated cardiovascular events (e.g., major adverse cardiovascular event [MACE]), lipid profile changes, anemia, neutropenia, lymphopenia, increased serum creatinine and renal dysfunction, hepatic events and increased hepatic transaminases, elevated CPK and non-cardiac, non-CNS embolic and thrombotic events) will be summarized. Event rate (per 100 patient years) for AEs of special interest will also be summarized for the combined safety analysis of Period 1 and Period 2.

---

All AEs leading to discontinuation of study drug will be presented in listing format. A listing by treatment group of TEAEs grouped by SOC and MedDRA preferred term with subject identification numbers will be generated.

#### **8.1.5.2.2 Serious Adverse Events and Death**

All treatment-emergent SAEs and AEs leading to death will also be presented in listing format. In addition, SAEs will be summarized by SOC and MedDRA PT.

#### **8.1.5.3 Analysis of Laboratory, Vital Sign, and ECG Data**

Changes from baseline by visit, and changes from baseline to minimum value, maximum value, and final values in continuous laboratory data, and vital signs will be summarized by treatment group.

Baseline values are defined as the last non-missing measurements recorded on or before the date of the first dose of study drug in Period 1.

The laboratory data will be categorized as Grade 1, Grade 2, Grade 3 and Grade 4 according to OMERACT criteria (Rheumatology Common Toxicity Criteria V.2.0). For creatine phosphokinase and serum creatinine, NCI CTC criteria will be used. The shift tables will tabulate the number and percentage of subjects with baseline and post-baseline values by grade level.

Listings will be provided for potentially clinically significant laboratory values and vital signs.

#### **8.1.6 Pharmacokinetic and Exposure-Response Analyses**

Individual upadacitinib plasma concentrations at each study visit will be tabulated and summarized with appropriate statistical methods.

Data from this study may be combined with data from other studies for the population PK and exposure-response analyses. Population PK and exposure-response analyses of only

data from this study may not be conducted. The following general methodology will be used for the population PK and exposure-response analyses.

Population PK analyses will be performed using the actual sampling time relative to dosing. PK models will be built using a non-linear mixed-effects modeling approach with NONMEM software (Version 7, or a higher version). The structure of the starting PK model will be based on the PK analysis of data from previous studies. The CL/F and V/F of upadacitinib will be the PK parameters of major interest in the analyses. If necessary, other parameters, including the parameters describing absorption characteristics, may be fixed if useful in the analysis.

The evaluation criteria described below will be used to examine the performance of different models.

1. The objective function of the best model is significantly smaller than the alternative model(s).
2. The observed and predicted concentrations from the preferred model are more randomly distributed across the line of unity (a straight line with zero intercept and a slope of one) than the alternative model(s).
3. Visual inspection of model fits, standard errors of model parameters and change in inter-subject and intra-subject error.

Once an appropriate base PK model (including inter- and intra-subject error structure) is developed, empirical Bayesian estimates of individual model parameters will be calculated by the posterior conditional estimation technique using non-linear mixed effects modeling. The relationship between these conditional estimates CL/F and V/F values with only potentially physiologically relevant or clinically meaningful covariates (such as subject age, sex, body weight, concomitant medications, laboratory markers of hepatic or renal function, etc.) will be explored using stepwise forward selection method, or another suitable regression/smoothing method at a significance level of 0.05. After identification of all relevant covariates, a stepwise backward elimination of covariates

from the full model will be employed to evaluate the significance (at  $P < 0.005$ , corresponding to a decrease in objective function  $> 7.88$  for one degree of freedom) of each covariate in the full model.

Linear or non-linear relationships of primary PK parameters with various covariates will be explored.

Relationships between upadacitinib exposure and clinical observations (primary efficacy variable) will be explored. Exposure-response relationships for secondary efficacy variables and/or some safety measures of interest may also be explored. The relationship between exposure (e.g., population PK model predicted average concentrations, area under the curve, trough concentrations, the individual model-predicted PK profiles, or some other appropriate measure of exposure) and drug effect will be explored. Several classes of models (e.g., linear, log-linear, exponential,  $E_{max}$ , sigmoid  $E_{max}$ , etc.) will be evaluated to characterize the exposure-response relationship based on observed data. Results of the PK and exposure-response analyses may be summarized in a separate report prior to regulatory filing of upadacitinib for the treatment of RA, rather than in the CSR.

Additional analyses will be performed if useful and appropriate.

#### **8.1.7                    Statistical Analysis of Biomarker Data (except for subjects in mainland China)**

Summary statistics for the in vivo pharmacodynamic biomarkers (including but not limited to NK, NKT, B cells, and T cells) at baseline and post-treatment time points (Weeks 8 and 12/PD in Period 1, and Weeks 16, 24, 36, 48 and 64/PD in Period 2), in addition to change from baseline at each time will be provided; this will include mean, standard deviation, median, quartiles, and range for each group. The pharmacodynamic effect of each biomarker between the placebo and upadacitinib treatment groups will be evaluated via a non-linear mixed-effects modeling approach with Change from baseline of the biomarker as response variable, Treatment, Time, and Treatment  $\times$  Time interaction as fixed-effects, the corresponding baseline biomarker score as a covariate, and "subjects nested within the treatment group" as a random-effect. Other baseline variables such as

age, weight, etc., may be considered as appropriate. For biomarkers identified to have significant overall treatment effect via the non-linear mixed effects modeling analysis, dose-response models with the biomarker as a continuous response will be explored. In addition to the above analyses of biomarkers individually, the effect of certain combination of biomarkers on the treatment groups may be explored.

If the optional exploratory research variables including an additional panel of prognostic, predictive, and pharmacodynamic biomarkers are evaluated, then those data may be analyzed as follows. The association of biomarkers to the efficacy and safety endpoints may be explored for each biomarker one at a time, and also for combinations of biomarkers via some multivariate predictive modeling algorithms. Optimal multivariate combinations of biomarkers that associate with efficacy endpoints, subject response/non-response (with respect to appropriate clinical endpoints), and also with safety endpoints may be explored via a variety of statistical predictive modeling algorithms. Also cut-points for individual biomarkers and optimal combinations of biomarkers that differentiate the subject response with respect to efficacy/safety endpoints may be explored. The significance of these multivariate combinations of biomarkers may be assessed via at least 20 iterations of 5 fold cross-validation.

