- s. At Screening only. For mainland China only, subjects with HBs Ab+ and/or HBC Ab+ and negative HBV DNA at screening, HBV DNA PCR test should be performed every 12 weeks. HBV DNA PCR testing every 12 weeks is not necessary when the subject has a history of HBV vaccine and HBs Ab+.
- t. Subjects will be tested for antibodies to HIV at Screening. The results of the HIV Ab testing will be retained by the study site under confidential restriction.
- u. At Week 1 and Week 2 visits, PK samples should be collected prior to dosing and the subjects should take the study drug dose at the clinic after collecting the PK blood sample. However, if the subject normally takes the study drug dose at a time that is after the time of the scheduled study visit, the subject should follow the regular dosing schedule and the PK sample should be collected at any time during the visit.
- v. PK samples should be collected at any time during the visit. Subject should follow the regular dosing schedule.
- w. In Vivo Pharmacodynamic biomarkers will not be collected for subjects in mainland China.
- x. Samples only collected if subject provides written consent and if not prohibited by local regulations. Optional samples for Exploratory Research and Validation Studies will not be collected for subjects in mainland China.
- y. For subjects entering Period 2.
- Note: Visit window is  $\pm 3$  days for Period 1. Any of the procedures may be performed at an unscheduled visit at the discretion of the Investigator.

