**5.3.6.2        Exploratory Research Variables and Validation Studies**

Where not prohibited by local regulations, optional samples may be collected to conduct exploratory investigations into known and novel biomarkers. The types of biomarkers to be analyzed may include, but are not limited to nucleic acids, proteins, lipids, or metabolites.

Optional samples for Exploratory Research and Validation Studies will not be collected for subjects in mainland China.

Biomarker assessments may be used to assess and generate prognostic, predictive, pharmacodynamic, or surrogate biomarker signatures. These assessments may be explored in the context of RA or related conditions and/or upadacitinib or drugs of similar classes. The results from these analyses are exploratory in nature and may not be included with the clinical study report (CSR).

The samples may also be used to develop new therapies, research methods or technologies. In addition, samples from this study may be stored for future use. Samples may then be used to validate putative biomarker signatures obtained from a prospective study, leading to the development of diagnostic tests.

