### **8.3 Randomization Methods**

Subjects will be randomly assigned in a 1:1 ratio to one of the two treatment groups. As indicated below, it is expected that approximately 222 subjects will enter the study from China and 100 subjects from other countries including Brazil and South Korea:

- Group 1: Upadacitinib 15 mg QD (N = 161; 111 from China) (Period 1) → Upadacitinib 15 mg QD (Period 2)
- Group 2: Placebo (N = 161; 111 from China) (Period 1) → Upadacitinib 15 mg QD (Period 2)

Randomization will be stratified by country and the Chinese population will be up to 80% of the total study population.

See Section [5.5.3](#) for details.

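### Repeated cross-validation is the only stated way to assess the significance of optional biomarker combinations, and it supplies no null distribution, so any significance claim read from it is uncalibrated

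*Protocol*

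**What the plan says.** Protocol Section 8.1.7 gives the lymphocyte-subset markers a mixed model. The optional panel, if it is evaluated at all, may be searched one marker at a time and in combination, against efficacy, responder status and safety endpoints. The best combinations "may be explored via a variety of statistical predictive modeling algorithms". On thresholds: "Also cut-points for individual biomarkers and optimal combinations of biomarkers that differentiate the subject response with respect to efficacy/safety endpoints may be explored". The paragraph ends: "The significance of these multivariate combinations of biomarkers may be assessed via at least 20 iterations of 5 fold cross-validation".

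That last sentence gives no test statistic, level, threshold, hold-out set, permutation or multiplicity rule. Nor does it say whether the choices of markers, algorithm and cut-point are repeated within each training fold. By contrast, the population PK covariate search in Section 8.1.6 has stated levels (0.05 forward, 0.005 backward).

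On the sample, a footnote to Protocol Table 3 says: "Optional samples for Exploratory Research and Validation Studies will not be collected for subjects in mainland China". Section 8.3 expects that "222 subjects will enter the study from China and 100 subjects from other countries including Brazil and South Korea". Table 4 lists pharmacogenetic, epigenetic, transcriptomic and proteomic samples but no panel sizes.

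On status, Section 5.3.6.2 labels the results exploratory and allows them to be left out of the study report. Section 12.0 calls them unfit to guide patient care. SAP Section 3.0 refers biomarker analyses to a separate plan. Section 5.3.6.2 also foresees a later use: "Samples may then be used to validate putative biomarker signatures obtained from a prospective study, leading to the development of diagnostic tests".

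**The concern.** Judging significance requires knowing how the chosen performance measure behaves when no marker is related to outcome. Repeated cross-validation does not supply this. Each iteration re-splits the same subjects, so the spread over 20 iterations reflects only how the folds happened to fall. More iterations narrow that spread without adding information.

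Two separate problems can follow. If selection is done inside the folds, a rule that treats the iterations as independent evidence, or that reports the best of several combinations, is too liberal. If the combinations are found on all the data and then cross-validated, the held-out subjects have already helped to choose them, and performance looks good even for noise.

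At stake is which signatures are labelled significant and carried into validation work or into aggregate publications, which Section 12.0 permits. The setting is unfavourable: few subjects against potentially wide panels.

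**Working it through.** **The plan's own figure.** Section 8.1.7 states no error rate. The nearest figure that can be reproduced is the ACR20 power in Section 8.2, which also supplies the response rates used below. With p1 = 0.367, p2 = 0.367 + 0.217 = 0.584 and n = 161 × 0.9 ≈ 145 per arm:

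- mean p = 0.4755; SE0 = √(2 × 0.4755 × 0.5245 / 145) = 0.0587
- SE1 = √((0.367 × 0.633 + 0.584 × 0.416) / 145) = 0.0573
- power = Φ((0.217 − 1.96 × SE0) / SE1) = Φ(1.78) = 96.3% (97.6% with 161 per arm)

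The stated power of over 90% is confirmed.

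**Inputs for the simulations.**

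- Subjects: 322 − 222 = 100 expected outside China, about 50 per arm, before optional consent. This is an expectation, not a ceiling. At the 80% China cap it would be 0.2 × 322 ≈ 64.
- Response rate: about 47.5%, the mean of 36.7% and 58.4%.
- Assumed, because the documents are silent: panel size, number of markers selected, performance measure, 5% level and decision rule.

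**Simulation A: selection inside the folds.** Markers are independent noise and response is random. In each training fold, d_j = mean of marker j in responders minus mean in non-responders. The k markers with the largest |d_j| are kept, the score is Σ d_j x_j, and AUC is computed in the held-out fold. This used 20 iterations of 5-fold cross-validation and 600 simulated trials per row. Figures are the percentage of trials in which noise was called significant:

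| n | markers / kept | t-test, 100 fold AUCs | t-test, 20 iteration means | 2.5th percentile of 20 AUCs > 0.5 | any of 20 p < 0.05 | median of 20 p < 0.05 |
|---|---|---|---|---|---|---|
| 50 | 10 / 3 | 43.0 | 44.3 | 21.5 | 36.5 | 11.5 |
| 50 | 50 / 5 | 34.2 | 34.8 | 14.5 | 37.3 | 8.5 |
| 50 | 200 / 10 | 37.8 | 38.0 | 14.7 | 42.5 | 9.3 |
| 100 | 10 / 3 | 39.2 | 40.3 | 18.2 | 35.2 | 8.0 |
| 100 | 50 / 5 | 38.3 | 38.7 | 14.7 | 41.0 | 9.2 |
| 100 | 200 / 10 | 36.0 | 35.5 | 13.5 | 41.2 | 8.5 |

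The t-tests are two-sided at 5% and counted only when AUC exceeds 0.5. The last two rules use one-sided rank-sum p-values. The Monte Carlo SE is √(0.1 × 0.9 / 600) = 1.2 points at 10% and √(0.4 × 0.6 / 600) = 2.0 points at 40%.

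**Simulation A: selection on all data first.** With n = 100 and 50/5 or 200/10 markers (300 trials each), 99.7% to 100% were called significant under every rule.

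**Simulation B: a different statistic.** This used a least-squares score on top-ranked markers, a one-sided t-test of pooled held-out scores, the median p over 20 iterations, 50 to 100 subjects, 20 to 1000 markers and 50–75% responders (100 to 300 trials per setting).

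- Inside folds, one pre-fixed size: 5–10%.
- Inside folds, best of four sizes (1, 3, 5, 10): 10–12.5%.
- Selection on all data first: 53% with 20 markers, 98% with 50, 100% with 200 to 1000.

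**Permutation check.** Outcomes are shuffled, the whole selection and cross-validation are rerun, and p = (1 + number of permuted results ≥ observed) / (99 + 1). In the setting of A (n = 100, 50 markers, 4 iterations, 200 trials), noise was called significant 4.5% of the time (SE 1.5 points). In the setting of B (2 iterations) the figure was 2–6.5%. With three true markers at 0.7 SD, n = 100 and 200 markers, power was 81%, against 93% for the uncalibrated best-of-four rule.

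**The case against.** The strongest reply is that the protocol commits to very little. The analysis is conditional on the panel being evaluated, and significance only *may* be assessed this way. A reader might infer that the plan will declare signatures significant from cross-validation. The text does not go that far, although it offers no alternative.

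The separate biomarker plan may define nested selection, a statistic and a valid null. It was not among the documents, so this can be neither credited nor ruled out.

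The simulated rates depend on rules supplied here, not by the sponsor. That stands: they are conditional illustrations, not a measured error rate for this trial. A reader might also infer that the search would almost always produce a significant combination. That holds only if markers are chosen on all data before cross-validation and many are searched. The protocol's sentence order permits that reading but does not state it.

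Harm is bounded too. The results are exploratory and not for patient care, and signatures are called putative and face validation before any diagnostic use. It would be wrong to read the reference to diagnostic tests as showing that such tests would rest on unvalidated noise.

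What remains is narrow but sound. Exploratory status excuses the absence of multiplicity control; it does not turn a performance estimate into a test.

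**Conclusion.** The concern holds as a point of method in one sentence of Protocol Section 8.1.7. Cross-validation is a reasonable way to estimate predictive performance, but it cannot by itself support a statement of significance.

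At a nominal 5%, the simulated false-positive rate is about 5–12% with selection inside the folds and a median-p rule, 14–44% under the other simple rules tried, and about 50–100% with selection on all data first. These ranges rest on independent noise markers, a binary response, 50 to 100 subjects, and assumed panel sizes and decision rules.

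No primary or ranked endpoint is touched. This is a low-priority improvement, worth making because it is cheap.

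**What to change.** In Section 8.1.7, and in the separate biomarker plan, replace the sentence with wording to this effect:

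- Repeated cross-validation will be reported as an estimate of predictive performance.
- Marker selection, algorithm choice and cut-point choice will be repeated inside every training fold.
- Any claim of significant association with outcome will come from permuting outcome labels within treatment group and country, rerunning the complete search and cross-validation on each permuted dataset, and comparing observed performance with that distribution.

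Permuting within treatment group matters because Table 4 includes post-baseline samples, so treatment can move both marker and outcome. The permutation checks above used few cross-validation iterations, and the 4.5% run shuffled without strata. The restricted version should be checked when the plan is written.

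A predictive (treatment-by-marker) claim needs its own stated null. Permuting outcomes within treatment group breaks every marker–outcome link and so cannot separate predictive from prognostic signatures.

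If no significance claim is intended, replacing the word significance with predictive performance is enough.

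The cost is a few sentences and computing time, with no new subjects or data. Fewer signatures will be called significant, with some loss of nominal power (81% against 93% in the example above).
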